**CONFIDENTIAL**

The information contained herein may not be used, disclosed, or published without the written consent of Biogen Italia

**Visit Schedule:** Baseline T0: start of treatment with Peg IFN beta-1a.  
T1: 12 weeks of treatment with Peg IFN beta-1a.  
T2: 24 weeks of treatment with Peg IFN beta-1a.  
ET (Early Termination): in case of early termination of the study.  
See flow chart.

**Planned duration of Treatment and Follow-up:** First Subject In (FPI): Sept/2015  
Last Subject In (LPI): Sept/2016  
Last Subject Last Visit (LPLV): March 2017

**Criteria for Evaluation:** *Inclusion criteria*  
18 ≤ Age ≤ 65 years  
RRMS as per 2010 McDonald criteria  
Baseline EDSS between 0.0 and 5.0  
Treatment with injectable subcutaneous Interferons with score < 58 in the "convenience satisfaction" domain of TSQM-9  
Signed informed consent  
Period of stability from last relapse of at least 30 days before the baseline visit.  
Treatment with intravenous corticosteroids completed at least 30 days before the baseline visit (assumption of oral cortisone allowed as long as within 4 mg per day for no longer than 3 days).

*Exclusion criteria*

Pregnancy or breast-feeding  
Depression or other psychiatric disorders  
Unwillingness or inability to comply with the protocol requirements  
Any contra-indications to treatment with Peg-IFN-beta 1a according to the Summary of Product Characteristics

**Efficacy:** Being this is a health outcomes research study, in the present protocol the term *efficacy* is referred to the

CONFIDENTIAL

The information contained herein may not be used, disclosed, or published without the written consent of Biogen Italia

assessment of the following patients' reported parameters, corresponding to the primary and secondary objectives of the study, and to the measurement of the related endpoints:

- overall treatment satisfaction,
- injection system satisfaction,
- adherence to treatment,
- health-related quality of life,
- fatigue.

*Safety:* Treatment tolerability will be assessed and all adverse events occurring during the study and changes in laboratory parameters will be collected. Also pregnancy and episodes of overdose will be collected.

*Additional:* Not applicable.

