#### **6.2.2. Secondary Endpoints**

- Changes from baseline in the score of all domains of TSQM-9 at 24 weeks;
- Changes from baseline in patient adherence to study treatment survey at 12 and 24 weeks;
- Changes from baseline in the score of FSS (Fatigue Status Scale) at 12 and 24 weeks;
- Changes from baseline in the score of Adapted Sclerosis Treatment Concerns Questionnaire (MSTCQ) at 12 and 24 weeks;
- Changes from baseline in the score of Multiple Sclerosis International Quality of Life questionnaire (MusiQoL) at 12 and 24 weeks;

- Changes from baseline in clinical measures (ARR, percentage of relapse-free patients), measures at 24 weeks.
- Incidence and severity of adverse events occurred during the study (including local tolerance to treatment at the injection site).
- Abnormalities in laboratory values.

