The primary endpoint is to evaluate the changes from baseline in the score of convenience satisfaction domain of TSQM-9 at 12 weeks. (*Stata instruction: anova var1 time, repeated(time)*)

b. Secondary Endpoints Analysis

- Changes from baseline in the score of all domains of TSQM-9 at 24 weeks;
- Changes from baseline in patient adherence to study treatment survey at 12 and 24 weeks;
- Changes from baseline in the score of FSS (Fatigue Status Scale) at 12 and 24 weeks;
- Changes from baseline in the score of Adapted Sclerosis Treatment Concerns Questionnaire (MSTCQ) at 12 and 24 weeks;
- Changes from baseline in the score of Multiple Sclerosis International Quality of Life questionnaire (MusiQoL) at 12 and 24 weeks;
- Changes from baseline in clinical measures (ARR, percentage of relapse-free patients), measures at 24 weeks.

All the above primary and secondary endpoints will be analysed by a repeated measures analysis of variance adjusted for baseline factors (age, sex, disease duration, previous treatment duration, EDSS) (*Stata instruction: anova var1 var2 time, repeated(time)*).

Correlations between variables will be assessed by a Spearman rank correlation coefficient (*Stata instruction: spearman var1 var2*).

[figure not shown]
To evaluate the relationship between patients' satisfaction and social-demographic factors (age, sex, employment working, level of education, etc.) and clinical characteristics (ARR, disability, etc.) generalized linear mixed models for repeated measurements will be performed (*Stata instruction: mixed var1 var2 || patient:*).

12. Safety Data

a. Adverse events

All events will be coded using the Medical Dictionary for Regulatory Activities (MedDRA). Type and incidence of all AEs will be tabulated. Severity and drug relatedness of all reported AEs will be tabulated.

b. Clinical Laboratory Tests

	Statistical Analysis Plan Protocol N. BIIT0215– Platinum	Pag. 14 di 18
---	---	---------------

For the clinical laboratory data, descriptive statistics will be generated for all tests performed. Laboratory abnormalities will be determined in accordance with the normal ranges of the clinical laboratory. Laboratory abnormalities will be tabulated.

13. Tables

The following tables will be repeated for each visit, if applicable.

- P1. Number and percentage of patients enrolled per center
- P2. Number and percentage of patients stratified by gender; mean and median age, range and interquartile range;

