P21. Number and percentage of patient who have correctly taken the prescribed doses of treatment within the last 28 days; if don't, mean and median, interquartile range and range of injections have not been performed during the last 28 days;

P22. Number and percentage of patients per reasons to non correctly taken the treatment:

- a) Anxiety for injection
- b) Skin reaction
- c) Forgot to take the dose
- d) Pain at the injection site

- e) Depression
- f) Headhache
- g) Fatigue
- h) Flu-like symptoms
- i) “I did not want to”
- j) “I am not sure of the benefits”
- k) “I am tired of injections”
- l) No one available for injection
- m) Uncomfortable dosing
- n) “I am pregnant / I have planned a pregnancy”
- o) Other

- P23. Mean and median, interquartile range and range of injections expected from the therapy taken in the last 28 days;
- P24. Mean and median, interquartile range and range of MSTCQ;
- P25. Change from baseline in the score of the MSTCQ at 12 and 24 weeks;
- P26. Adjusted repeated measures analysis of variance for change of the MSTCQ at 12 and 24 weeks;
- P27. Mean and median, interquartile range and range of MusiQol;
- P28. Change from baseline in the score of the MusiQol at 12 and 24 weeks;
- P29. Adjusted repeated measures analysis of variance for change of the MusiQol at 12 and 24 weeks;
- P30. Mean and median, interquartile range and range of FSS;
- P31. Change from baseline in the score of the FSS at 12 and 24 weeks;
- P32. Adjusted repeated measures analysis of variance for change of the FSS at 12 and 24 weeks;
- P33. Mean and median, interquartile range and range of EDSS;
- P34. Change from baseline in the score of the EDSS at 12 and 24 weeks;
- P35. ARR, Annualized Relapse Rate
- P36. Number and percentage of abnormalities in laboratory values per each test;
- P37. List of all laboratory abnormalities;
- P38. Number and percentage of adverse events stratified by severity;

	
Statistical Analysis Plan Protocol N. BIIT0215– Platinum
	
Pag. 18 di 18

--	---	---

- P39. List of all adverse events with related characteristics;
- P40. Number and percentage of patients who discontinued the study and reasons of discontinuity;
- P41. Number and percentage of patients who experienced pregnancy during the study and outcome of pregnancy.

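### The only adverse-event summary in the SAP table list counts events by severity; no patient-level incidence table is listed, and serious and injection-site events have no dedicated summary

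*SAP*

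**What the plan says.** Protocol 6.2.2 lists as a secondary endpoint "Incidence and severity of adverse events occurred during the study (including local tolerance to treatment at the injection site", and separately "Abnormalities in laboratory values". Protocol 16.4.1 sets a patient-based safety population, the All Patients Treated Set (APTS). SAP section 5 names only the Full Analysis Set (FAS), but the two definitions are the same: every enrolled patient who took any dose.

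For the analysis, SAP 12.a repeats Protocol 16.4.2: "Type and incidence of all AEs will be tabulated. Severity and drug relatedness of all reported AEs will be tabulated". It defines neither the unit nor the denominator, and it mentions neither seriousness nor the injection site.

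The outputs are in SAP section 13. For adverse events they are "P38. Number and percentage of adverse events stratified by severity" and P39, a listing of all events with their characteristics. For laboratory data they are "P36. Number and percentage of abnormalities in laboratory values per each test" and P37, a listing. Section 13 opens by saying that tables are repeated by visit where applicable. Pregnancies have a table (P41). Overdoses do not, although the synopsis says "Also pregnancy and episodes of overdose will be collected".

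**The concern.** Incidence, in a safety endpoint defined on treated patients, means how many patients had an event. P38 counts events. With an injection every two weeks, the same mild reaction can recur in one patient many times. Each recurrence that is entered separately raises the number of mild events and lowers the percentage shown as severe, with no change in any patient's risk. The percentage would then partly measure recording habits at the 35 sites.

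Local tolerance is the only kind of event that the endpoint names, yet no adverse-event output is dedicated to it. Seriousness must be judged for every event under Protocol 15.2.4, yet it has no planned summary either. SAP section 1 says the results are for publication, so a programmer who follows the list literally would supply a safety table that readers could take for patient risk.

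**Working it through.** The documents state no figure on this point, so there is none to reproduce. The check is a comparison of texts, followed by an illustration.

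**Step 1. Endpoint, analysis text and tables side by side.**

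| Item | Protocol 6.2.2 | SAP 12.a | SAP 13 |
|---|---|---|---|
| Patients with at least one event | incidence | incidence, unit undefined | no table |
| Type (MedDRA term) | not named | yes | no summary; P39 lists events |
| Severity | yes | yes | P38, at event level |
| Relatedness | not named | yes | no summary |
| Seriousness | not named | no | no summary |
| Injection-site events | named | no separate mention | no adverse-event summary |

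**Step 2. Is the unit in P38 what it seems?** P1 to P5, P7, P8, P11, P12, P21, P22, P40 and P41 all count patients. P11 changes from patients to diseases within a single entry, so the list does distinguish units. P38 names events as its unit and gives no denominator. The literal reading is a percentage of events.

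**Step 3. What an event percentage can hide (illustrative counts, all assumed).** Let 275 patients be treated and let 28 of them have exactly one severe event each. The patient risk of a severe event is 28/275 = 10.2%.

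- With 250 non-severe events recorded, the severe share of events is 28/(28 + 250) = 28/278 = 10.1%.
- With 2,500 non-severe events recorded, it is 28/(28 + 2,500) = 28/2,528 = 1.1%. That many would arise if about 208 patients had one mild event entered after each of 24/2 = 12 injections (208 × 12 = 2,496).
- If the denominator were patients instead, the non-severe row would read 250/275 = 90.9% or 2,500/275 = 909.1%. The second cannot be a proportion of patients.

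Nor can patient incidence be recovered from P38. In the first case (278 events), the number of patients with any event could be as low as 28, if all the other events fell in the same 28 patients. It could be as high as 275, because 250 events are enough to cover the remaining 275 − 28 = 247 patients. One and the same P38 therefore fits an incidence anywhere from 10.2% to 100%.

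A table by type built on the same unit would behave alike. Assume 60 of 275 patients (21.8%) with an injection-site reaction, and 100 other events. With 1, 3 or 6 reactions per affected patient, these reactions make up 60/160 = 37.5%, 180/280 = 64.3% or 360/460 = 78.3% of events. The patient incidence stays at 21.8%.

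**Step 4. P36.** It is given per test, and section 13 repeats tables by visit. With one result per test and visit, the number of abnormalities equals the number of patients with an abnormality, so the unit does little harm. The denominator does need stating. Protocol 4.2 schedules laboratory tests at every visit, but Protocol 14.2 and SAP section 8 leave them to the investigator's discretion, so the number tested may vary.

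**The case against.** The strongest reply is that SAP 12.a already commits to "Type and incidence of all AEs will be tabulated", and to severity and relatedness as well. Section 13 does not claim to be exhaustive, and section 1 describes the plan as general guidance. The proportion free of relapse is also an endpoint without a table, which suggests an incomplete list and not a decision to drop outputs. This stands. A reader might infer that the incidence endpoint will not be produced, and the documents do not support that. What they show is that section 13 does not carry section 12 through at patient level, and that section 12 itself leaves the unit open.

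Second, severity is covered by P38, and the P39 listing may hold term, relatedness and seriousness. That is true, but a listing is not a summary, and P38 gives severity only by event.

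Third, local tolerance is not wholly absent. Injection-site events would be coded and fall under the promised tabulation by type. The MSTCQ analysed in P24 to P26 has an injection-site subscale, and P22 counts skin reaction and injection-site pain as reasons for missed doses. So it would be wrong to say there is no information. However, P24 to P26 do not name the subscale, and neither source gives the incidence of injection-site adverse events.

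Fourth, P38 states no denominator, the SAP's English is loose in places, and no document says that a recurrent reaction is entered as a new event each time. All of this is fair. The event denominator is the literal reading but not a certainty, and the swing in Step 3 is only an example.

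Two wider readings also fail. A reader might want overdoses in the same tables, but Protocol 15.5.1 says that they are not adverse events. A reader might want laboratory shift tables, but the endpoint asks only for abnormalities, and discretionary testing may leave baseline values missing.

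**Conclusion.** The point holds in a limited form. SAP 12.a promises type, incidence, severity and relatedness. The table list turns this into one event-level summary by severity and a listing. An event percentage is the wrong unit for an incidence endpoint on treated patients. No patient-level table is listed, and serious and injection-site events have no dedicated summary in section 12 or 13.

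The size cannot be taken from the documents. The drop from 10.1% to 1.1% at a constant patient risk of 10.2% is illustrative. It rests on assumed counts, on an event denominator and on recurrent events being recorded separately. What needs no assumed counts is that a percentage of events cannot be turned into a percentage of patients once events can recur. The primary endpoint and the sample size are unaffected. This is worth correcting before the tables are programmed.

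**What to change.** In SAP section 13, replace P38 with the number and percentage of treated patients with at least one adverse event over the whole study. Show it overall and by MedDRA system organ class and preferred term, with each patient counted once at maximum severity, and give event counts in a second column. Name the APTS as the denominator; its definition matches the FAS, so the number of patients does not change. Give the same table for related events, serious events and injection-site reactions, and say in advance which MedDRA terms count as injection-site reactions. Add seriousness and injection-site events to the text of section 12.a so that the two sections agree.

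State the P36 denominator as patients tested for that parameter at that visit. Add a simple count of overdoses. P39, P40 and P41 can stay as they are.

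The cost is an edit to the SAP and a few standard tables. The protocol already requires seriousness, relationship and severity to be assessed for every event and all events to be MedDRA-coded, so no new data collection appears to be needed.
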